4.5.2 Medical History, Concomitant Medication, and Demographic Data

Medical history, including clinically significant diseases, surgeries, cancer history (including prior cancer therapies and procedures), reproductive status, smoking history, and use of alcohol and drugs of abuse, will be recorded at baseline. In addition, all medications (e.g., prescription drugs, over-the-counter drugs, vaccines, herbal or homeopathic remedies, nutritional supplements) used by the patient within 28 days prior to initiation of study treatment will be recorded. At the time of each follow-up physical examination, an interval medical history should be obtained and any changes in medications and allergies should be recorded.

Demographic data will include age, sex, and self-reported race/ethnicity.

For patients enrolled in the post-consolidation cohort, all details with regards to their previous AML history and treatment will be collected including but not limited to dates, medications, regimens, and responses

4.5.3 Physical Examinations

A complete physical examination should be performed at screening and should include an evaluation of the head, eyes, ears, nose, and throat, and the cardiovascular, dermatologic, musculoskeletal, respiratory, GI, genitourinary, and neurologic systems. Any abnormality identified at baseline should be recorded on the General Medical History and Baseline Conditions eCRF.

At subsequent visits (or as clinically indicated), targeted (limited, symptom-directed) physical examinations should be performed. Targeted physical examinations should be limited to systems of primary relevance (e.g., cardiovascular and respiratory systems), systems associated with symptoms (newly emergent or monitored from baseline).

Changes from baseline abnormalities should be recorded in patient notes. New or worsened clinically significant abnormalities should be recorded as adverse events on the Adverse Event eCRF.

In cases that physical examinations reveal visible manifestations of leukemia or of toxicities (skin involvement, rashes, etc.), additional assessments and measures (such as pictures and measurements) could be undertaken upon additional patient consent.

4.5.4 Performance Status

Performance status will be measured using the ECOG performance status at baseline and will be assessed at regular intervals throughout the study. Further details can be found in [Appendix 1](#) and [Appendix 3](#).

4.5.5 Vital Signs

Vital signs will include measurements of respiratory rate, pulse rate, and systolic and diastolic blood pressure while the patient is in a seated position, BSA, and body temperature (°C). Weight will be recorded at screening and as indicated in [Appendix 1](#). Height will be recorded only at screening.

4.5.6 Tumor and Response Evaluations

Hematologic malignancy response will be assessed according to ELN and additional response criteria for AML (see [Appendix 19](#)).

Hematologic malignancy response assessments (HMRA) require sampling of blood and bone marrow on the same day as indicated (a window of 4 days is acceptable between the blood and bone marrow sampling). Bone marrow aspirates are required, but if bone marrow biopsies are performed, the biopsy results should be provided along with the aspirate. Depending on the timepoint in the schedule of activities, the HMRA is established on the basis of blood counts only, or includes the assessment of bone marrow. Patients will be considered to be in their best response state until definitive evidence of relapse is available from blood counts, bone marrow aspirate, or bone marrow biopsy.

In the event that a bone marrow aspirate or biopsy is equivocal (i.e., a recovering marrow), the bone marrow assessment and complete blood count should be repeated > 7 days later.

In case disease progression/relapse is determined solely by symptomatic deterioration or by a hematology assessment, a bone marrow aspirate should be performed at that time to complete HMRA. If a patient progresses or relapses outside of the scheduled visit, an unscheduled HMRA must be provided.

If a bone marrow aspirate is performed at any unscheduled timepoint during the study, an unscheduled HMRA must be provided.

Please note that at the time of bone marrow sampling for HMRA, the bone marrow sample collected (aspirate) should also allow for further analyses (e.g., MRD by flow cytometry, MRD by NGS) and the amount taken should be taken into consideration.

During the treatment period, HMRA are to be performed and reviewed before the start of a new treatment cycle. In the event that a patient has a dosing delay > 7 days in consolidation or induction, weekly blood counts must be performed for HMRA to

document evidence of non-progression. Treatment failure and relapse will lead to discontinuation of the study medication and patients will enter follow-up (see [Appendix 1](#)).

During the follow-up of patients who remain in remission after treatment, blood will be required every month and a bone marrow aspirate will be required every 6 months to allow for HMRA until relapse. Refer to [Appendix 1](#) for further details.

4.5.7 Laboratory Assessments

Normal ranges for the study laboratory parameters must be submitted to the Sponsor before the study starts.

Samples for the following laboratory tests will be sent to the study site's laboratory for analysis.

- Hematology: WBC count, RBC count, hemoglobin, hematocrit, platelet count, differential count (neutrophils, eosinophils, basophils, monocytes, lymphocytes, blasts, promyelocytes, myelocytes, metamyelocytes)
 - A manual differential (including WBC) may be needed if an automated differential does not provide blasts. Each differential should add up to 100% (or as close as possible).
- Biochemistry: procalcitonin, glucose, urea or BUN, serum creatinine, creatinine clearance (at screening only determined by Cockcroft-Gault Formula), AST, ALT, LDH, ALP, total bilirubin (and direct bilirubin where total bilirubin > ULN), total protein, albumin, calcium, phosphorus, magnesium, sodium, potassium, bicarbonate, chloride, and uric acid)
- Urinalysis using standard dipstick assessment (pH, protein, glucose, blood, ketones, and leukocytes)
 - This must be supplemented with laboratory quantification of any potentially relevant abnormalities as deemed necessary by the investigator.
- *C. difficile* infection at screening
- Viral serology
 - Hepatitis B testing includes hepatitis B surface antigen and total hepatitis B core antibody.
 - Hepatitis C testing includes hepatitis C virus antibody.
- Coagulation: INR, aPTT (or PTT), and PT
- Serum pregnancy test in females of child bearing potential and postmenopausal females with less than 1 year of amenorrhea
- Bone marrow aspirate pathology report

Total cells counted, absolute mature neutrophils, mature eosinophils, mature basophils, monocytes, lymphocytes, blasts, promyelocytes, myelocytes, metamyelocytes, plasma cells, pronormoblasts, normoblasts, and nucleated erythrocytes

Quantitative and validated AML-specific MRD assessment at end of induction in the post-consolidation cohort

- Bone marrow biopsy (leukemia histology, cellularity, percent cellularity, percent blasts)

4.5.8 Mandatory Samples for Pharmacokinetic, Pharmacodynamic Biomarker, and Exploratory Biomarker Analyses

All samples listed below will be collected according to the schedule of activities outlined in [Appendix 2](#). Unscheduled PK samples matched to ECG recordings may be required in case any prolongation of the QTc interval or other adverse cardiac findings is identified (see Section [4.5.9](#) for details). For PK analysis, it is of utmost importance to record dosing and blood sampling times accurately.

For sampling procedures, storage conditions, and shipment instructions see the laboratory manual(s).

4.5.8.1 MRD Assessments for Patients in the Post-Consolidation Phase

Patients in the post-consolidation phase with an MRD-positive remission after induction will be enrolled after local MRD assessment with a validated quantitative AML specific method. In order to monitor MRD during maintenance, assessments will be performed at 3 monthly intervals (see [Appendix 1](#)).

4.5.8.2 Pharmacokinetic Analyses

PK blood samples will be collected in all patients according to the sample schedule outlined in [Appendix 2](#).

All PK samples will be collected from the arm (limb) that is not being used during the administration of IV drugs (i.e., from the alternate arm). If IV drugs are administered via a central line, PK samples may be collected via the same access after completely flushing the line.

In case a patient experiences an adverse event without plausible clinical explanation, the investigator may perform an additional blood draw for unscheduled PK analysis. Care should be taken to accurately record timing of blood sampling on the unscheduled PK sampling page of the eCRF.

All PK blood samples may be destroyed when the analysis is complete and the Bioanalytical Report finalized. Residual PK samples may be used for additional validation experiments as appropriate.

4.5.8.3 Pharmacodynamic and Exploratory Biomarkers

Bone marrow and blood samples will be collected from patients for pharmacodynamic and exploratory biomarkers. These samples will be tested for protein, nucleic acid, or other tumor cell–derived biomarkers relating to the proposed mechanism of action of idasanutlin, disease-associated markers, or improvement of diagnostic assays. Analysis to include, but are not limited to:

- Sequencing of cancer-related genes including TP53
- Measurement of transcript gene expression
- Protein expression in tumor cells by flow cytometry
- MRD in bone marrow

MRD will be monitored along clinical response assessments during induction, consolidation and maintenance. MRD will be assessed primarily by flow cytometry. Subsequent confirmation may use NGS panel following AML-specific mutations.

This research involves extraction of DNA, or RNA, analysis of mutations and genomic profiling through use of NGS for a comprehensive panel of genes. Research will not be aimed at distinguishing germline mutations from somatic mutations.

The specimens will also be used for research purposes to identify biomarkers useful for predicting and monitoring response to idasanutlin treatment, identifying biomarkers useful for predicting and monitoring safety, assessing pharmacodynamic effects of idasanutlin treatment, evaluating potential combination partners, and investigating mechanism of therapy resistance. Additional markers may be measured in case a strong scientific rationale for these analyses develops. On the basis continuous analysis of biomarker data any analysis, timepoint, or sample type not considered to be critical for safety may be stopped at any time if the data do not support a strong scientific justification to continue. Some samples that are collected may not be analyzed. Furthermore, some analysis may depend on patient's molecular status or response to treatment.

Unless the patient gives specific consent for his or her leftover samples to be stored for optional exploratory research (Research Biosample Repository; see Section 4.5.11), biologic samples will be destroyed when the final Clinical Study Report has been completed, with the following exceptions:

- Samples collected for biomarker research will be destroyed no later than 5 years after the final Clinical Study Report has been completed
- For enrolled patients, remaining archival tissue blocks will be returned to the site upon request or no later than the time of final closure of the study database, whichever occurs first. For patients who are not enrolled, remaining archival tissue blocks will be returned to the site no later than 6 weeks after eligibility determination.

When a patient withdraws from the study, samples collected prior to the date of withdrawal may still be analyzed, unless the patient specifically requests that the samples be destroyed or local laws require destruction of the samples. However, if samples have been tested prior to withdrawal, results from those tests will remain as part of the overall research data.

Data arising from sample analysis, including data on germline mutations, will be subject to the confidentiality standards described in Section 8.4.

Given the complexity and exploratory nature of exploratory biomarker analyses, data derived from these analyses will generally not be provided to study investigators or patients unless required by law. The aggregate results of any conducted research will be available in accordance with the effective Sponsor policy on study data publication.

4.5.8.4 Clinical Genotyping

DNA will be analyzed from whole blood for polymorphisms which may predict potential DDI and altered metabolism (such as *CYP* genes) of idasanutlin.

If the sample is missed on Day 1, it can be collected at any other scheduled visit. This specimen will be destroyed after analysis. Data arising from clinical genotyping samples will be subject to the confidentiality standards described in Section 8.4.

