During the dose-escalation phase, study treatment will be administered as outlined in [Table 1](#). Patients who achieve remission (CR, CRi, CRp, or CRh) after up to 2 induction cycles will receive chemotherapy consolidation treatment up to 4 cycles or allo-HSCT consolidation at the investigator's discretion. Patients who achieved a confirmed remission at the end of chemotherapy consolidation or allo-HSCT or who underwent allo-HSCT in MLFS after induction (see definition of MLFS in [Appendix 19](#)) will receive maintenance treatment for 12 cycles (see [Table 1](#)). In cases where the patient receives allo-HSCT consolidation, maintenance should start within 90 days of the transplant and a full pre-transplant hematologic response assessment must be provided if the transplant is performed more than 4 weeks after end of induction. Patients receiving chemotherapy consolidation should start maintenance right after completion of the consolidation. On the basis of safety, tolerability, and clinical benefit and after consultation with the Medical Monitor, patients may be allowed to continue maintenance at the same dose beyond 12 cycles. All patients will be followed for disease progression and survival. The dose for idasanutlin in consolidation will be determined by the Sponsor upon review of all available safety, PK, pharmacodynamic, and efficacy data. The dose for consolidation will not exceed the dose the patient received during induction.

After the last patient in each cohort has completed the DLT assessment window (first induction cycle), the Sponsor will evaluate the next dose recommended according to the mCRM (see Section [3.1.2.3](#)) and determine doses for the subsequent cohort(s), taking into account relevant demographic, adverse event, laboratory, dose administration, and PK (if available) data. At each dose-escalation step, the dose may be escalated or de-escalated, or an additional cohort at the same dose level may be enrolled.

On the basis of review of real-time safety data from this study and all available data from other studies in the program, dose escalation may be halted or modified by the Sponsor as deemed appropriate.

Although the DLT assessment window is defined as the first induction cycle, cumulative toxicities occurring beyond the first cycle may be considered when determining the MTD for idasanutlin. At the end of the dose-escalation phase, the idasanutlin RP2D in combination with cytarabine and daunorubicin will be decided.

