3.1.3 Post-Consolidation Phase and Expansion Phase

The post-consolidation cohort of 30 patients is designed to further assess the safety and efficacy of idasanutlin given as a single agent to idasanutlin treatment-naïve patients in a maintenance setting. Patients will start maintenance right after consolidation completion.

The expansion phase is designed to further assess the safety and efficacy of idasanutlin in combination with cytarabine and daunorubicin at its RP2D in induction and in combination with cytarabine in consolidation followed by a single-agent maintenance.

The expansion phase (approximately 40 patients) is composed of two cohorts: 20 patients with favorable or intermediate risk and 20 patients with high risk (see [Table 3](#)).

All expansion patients will be enrolled and treated as described in [Table 4](#), and patients in the post-consolidation cohort will receive maintenance treatment as described in [Table 5](#).

In the expansion cohorts, patients who achieve remission after up to 2 induction cycles will receive chemotherapy consolidation treatment up to 4 cycles with 1.5 mg/m² cytarabine or allo-HSCT (as per site guidelines). Patients who achieved a confirmed remission at the end of chemotherapy consolidation or allo-HSCT or who underwent allo-HSCT in MLFS after induction will receive maintenance treatment for 12 cycles (see [Table 4](#)).

Patients receiving chemotherapy consolidation in the expansion should start maintenance right after consolidation completion. Patients receiving allo-HSCT consolidation should start within 90 days of the transplant and a full pre-transplant hematologic response assessment must be provided if the transplant is performed more than 4 weeks after end of induction.

On the basis of safety, tolerability, and clinical benefit and after consultation with the Medical Monitor, patients may be allowed to continue maintenance past 12 cycles.

Table 3 Post-Consolidation and Expansion Cohorts

| Cohorts | Population |
|---|---|
| Post-consolidation | Idasanutlin treatment-naïve patients in remission who received chemotherapy consolidation but were MRD positive after induction as locally assessed |
| Expansion: favorable or intermediate risk | Favorable and intermediate risk patients (ELN 2017; see Appendix 8) |
| Expansion: high risk | Adverse-risk patients (ELN 2017; see Appendix 8) and secondary AML defined as AML evolving from AHD |

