Appendix 1: Schedule of Activities (cont.)

Table 3: Maintenance in the Dose-Escalation Cohort and Expansion

| Assessment/Procedure | Maintenance (28-Day Cycle; ± 2 days) All Cycles | | | | | | |
|--|---|----|----|----|----|----------------|----------------|
| | D1 | D2 | D3 | D4 | D5 | D15 | D28 (Q3M) |
| Vital signs ^a , weight, ECOG performance status | x | | | | | | |
| Single 12-Lead ECG ^b | x | | | | | | |
| Targeted physical examination ^c | x | | | | | | |
| Urinalysis | x | | | | | | |
| FACIT-Fatigue, EORTC Item Library, EQ-5D-5L ^d | x ^e | | | | | | |
| PRO-CTCAE, EORTC QLQ-C30 ^d | x | | | | | | |
| Biochemistry ^f | x | | | | | x ^g | |
| Hematology ^f | x | | | | | x ^g | |
| HMRA | x | | | | | | x |
| Bone marrow sampling for HMRA ^h | x ⁱ | | | | | | x |
| RBR sampling Blood serum, plasma (optional) | x | | | | | | |
| Bone marrow sampling for MRD/Flow, EDTA, PAXgene [®] ^j | x ⁱ | | | | | | x |
| Whole blood sampling for EDTA and clinical | x | | | | | | x ^k |
| PK sampling | Refer to Appendix 2 | | | | | | |
| Concomitant medications | To be recorded continually; see Section 4.4 | | | | | | |
| Adverse events | To be assessed continually; see Section 5.3.1 | | | | | | |
| Idasanutlin (PO QD) ^l | x | x | x | x | x | | |

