Appendix 1: Schedule of Activities (cont.)

Table 3: Maintenance in the Escalation Cohort and Expansion (cont.)

CTCAE=Common Terminology Criteria for Adverse Events; ECOG=Eastern Cooperative Oncology Group; eCRF=electronic Case Report Form; EDTA=ethylenediaminetetraacetic acid; EORTC=European Organisation for Research and Treatment of Cancer; EORTC QLQ-C30=EORTC Quality-of-Life Questionnaire–Core 30; EQ-5D-5L=EuroQol 5-Dimension, 5-Level; FACIT=Functional Assessment of Chronic Illness Therapy; HMRA=hematologic malignancy response assessment; MRD=minimal residual disease; PK=pharmacokinetic; PO=orally; PRO=patient-reported outcome; PRO-CTCAE=Patient-Reported Outcomes Common Terminology Criteria for Adverse Events; Q3M=once every 3 months; QD=once a day; RBR=Research Biosample Repository.

- ^a Vital signs include body temperature, systolic and diastolic blood pressure, pulse rate, and respiratory rate. Body surface area will also be measured at screening.
- ^b All ECGs should be performed within 2 hours prior to idasanutlin administration and 6 hours after idasanutlin administration.
- ^c Includes systems of primary relevance (e.g., cardiovascular and respiratory systems), systems associated with symptoms (newly emergent or monitored from baseline), and areas associated with tumor assessment (lymph nodes, liver, spleen, and any other areas identified at baseline). Record new or worsened clinically significant abnormalities on the Adverse Event eCRF.
- ^d PRO questionnaires need to be self-administered before the patient receives any information on disease status and prior to the administration of study treatment. Completion of PROs should occur prior to the performance of non-PRO assessments whenever possible. PRO assessments include the FACIT-Fatigue, EORTC QLQ-C30, EORTC Item Library symptoms, PRO-CTCAE, and EQ-5D-5L.
- ^e Every 3 months starting at Cycle 1.
- ^f All hematology and biochemistry assessments may be performed up to 3 days prior to the scheduled timepoint. Results must be reviewed by the investigator (or designee) PRIOR to study drug administration.
- ^g Only the first 3 cycles of maintenance.
- ^h For HMRAs during study, bone marrow aspirates are required, but bone marrow biopsies may be performed at the discretion of the investigator
- ⁱ Only required at maintenance Month 1 to confirm response in patients having received a transplant, bone marrow examination will require biopsy if an aspirate is not evaluable.

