Appendix 1: Schedule of Activities (cont.)

Table 5: Post-Treatment Phase

| Assessment/Procedure | Study Drug Discontinuation/Early Termination Visit 28 Days after Last Dose of Study Drug | Post-Tx Follow-Up Period | | Survival Follow-Up Period (Q3M) ^b |
|--|---|--------------------------------|--------------------------------|--|
| | | Q1M up to 2 Years ^a | Q6M up to 2 Years ^a | |
| Serum pregnancy test | x | | | |
| Triplicate 12-lead ECG | x | | | |
| Biochemistry | x | x | | |
| Hematology | x | x | | |
| Urinalysis | x | | | |
| HMRA | x | | x | |
| Bone marrow sampling for HMRA ^c | x | | x | |
| Bone marrow sampling (MRD/Flow, EDTA, PAXgene [®]) ^d | x | | x | |
| Whole blood sampling (EDTA, clinical) | x | x | | |
| FACIT-Fatigue, EORTC Item Library, PRO-CTCAE, EORTC QLQ-C30, EQ-5D-5L ^e | x | | | |
| Concomitant medications | x | | | |
| Adverse events | x | x | | |
| New leukemia treatment | | x | | x |
| Survival follow-up | | | | x |

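### The rule for a missed genotyping sample sets no pre-transplant limit, so blood drawn after allo-HSCT can give a CYP genotype that is not the patient's (small impact)

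*Combined protocol and SAP*

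**What the plan says.** Section 4.5.8.4 (Clinical Genotyping) names the specimen and its purpose: "DNA will be analyzed from whole blood for polymorphisms which may predict potential DDI and altered metabolism". The rule for a missed sample follows: "If the sample is missed on Day 1, it can be collected at any other scheduled visit". It carries no time limit and no exception for transplant. The same section says that the specimen is destroyed after analysis.

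Transplant is part of the planned treatment path. In dose escalation, patients in remission "will receive chemotherapy consolidation treatment up to 4 cycles or allo-HSCT consolidation" (Section 3.1.2.2). The expansion cohorts have the same option (Section 3.1.3). In both phases visits continue afterwards: "In cases where the patient receives allo-HSCT consolidation, maintenance should start within 90 days of the transplant" (Section 3.1.2.2) and "Patients receiving allo-HSCT consolidation should start within 90 days of the transplant" (Section 3.1.3). Appendix 1, Table 3 (maintenance) covers these patients explicitly, because a footnote to its bone marrow rows reads "Only required at maintenance Month 1 to confirm response in patients having received a transplant".

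The only instruction on sampling before transplant is in Section 4.5.8.5. It concerns bone marrow for MRD and biomarkers, where possible, and does not mention the genotyping blood sample.

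**The concern.** After engraftment, blood leukocytes are largely of donor origin, so DNA from whole blood mainly reports the donor's genotype. Drug metabolism in liver and gut still follows the patient's own genotype. This is general biology that the protocol does not state. A catch-up rule that is harmless in most trials is not safe here, because this protocol allows allo-HSCT between induction and maintenance.

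At stake is a wrong value rather than a missing one: a donor genotype stored against the patient's idasanutlin concentrations. Because the specimen is destroyed after analysis, that sample cannot be re-tested. Sections 3.1.1 and 3.3.2 explain that dose escalation was restricted to favorable and intermediate risk to keep down the number of patients going to transplant. Any exposure should therefore be greatest in the 20-patient high-risk cohort.

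**Working it through.** The protocol gives no figure for clinical genotyping, a transplant rate or a missed-sample rate, so there is nothing of the plan's own to reproduce. The first step is a cross-reading. The second is a bound on the size, using stated assumptions.

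**Does the rule reach post-transplant visits?**

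- Section 4.5.8.4 allows whole blood from any scheduled visit.
- Sections 3.1.2.2 and 3.1.3 allow allo-HSCT on study, followed by maintenance for 12 cycles.
- Appendix 1, Table 3 schedules maintenance visits for transplanted patients.
- No section requires the genotyping sample before transplant, names a non-blood germline source, or tells the analyst to flag post-transplant results.
- Post-consolidation patients are not exposed at entry, because previous HSCT is excluded (Section 4.1.2.3).

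The rule therefore permits post-transplant collection in the dose-escalation phase (9–15 evaluable patients, up to about 20 enrolled) and in the expansion phase (about 40).

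**How often would donor and patient differ?**

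Assume one biallelic variant in Hardy-Weinberg proportions, with minor allele frequency q of 10% or 20% and p = 1 − q.

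Unrelated donor: discordance = 1 − (p⁴ + 4p²q² + q⁴).

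- q = 0.1: 1 − (0.6561 + 0.0324 + 0.0001) = 0.311
- q = 0.2: 1 − (0.4096 + 0.1024 + 0.0016) = 0.486

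Sibling donor: discordance = 1 − [0.25 + 0.5(p³ + pq + q³) + 0.25(p⁴ + 4p²q² + q⁴)].

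- q = 0.1: 1 − [0.25 + 0.5(0.820) + 0.25(0.6886)] = 0.168
- q = 0.2: 1 − [0.25 + 0.5(0.680) + 0.25(0.5136)] = 0.282

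The range is 17% to 49%, so donor and patient share the genotype in 51% to 83% of pairs.

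**How many high-risk patients could be affected?**

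Assume that 5–20% miss Day 1 and 30–60% are transplanted, that the two are independent, and that nobody who misses Day 1 is sampled before transplant.

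- Sampled only after transplant: 20 × 0.05 × 0.30 = 0.3, to 20 × 0.20 × 0.60 = 2.4 patients
- Misclassified: 0.3 × 0.168 = 0.05, to 2.4 × 0.486 = 1.2 patients

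The assumption of no catch-up makes this an upper range for these inputs. Appendix 1, Table 1 schedules chemistry and hematology on Days 2, 5, 8, 15, 22 and 28 of each induction cycle, and a missed sample may be taken at any of those visits. If 10% of Day 1 misses stayed uncollected until transplant (also assumed), the range would fall tenfold, to about 0.005–0.12 patients.

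**The case against.** The strongest reply is that the gap hardly matters. An error needs a miss on Day 1 and at every later visit before transplant, and then a donor whose genotype differs. Genotype is not among the covariate examples for the population PK analysis in Section 3.3.3, and Sections 6.5 and 6.6 do not name it. The PK-interaction objective in Section 2.3 rests on plasma concentrations. All of this stands and limits the point to a minor one. It does not make the rule right. The covariate list in Section 3.3.3 is given as examples, and the exploratory objective in Section 2.4 refers to the biomarkers of Section 4.5.8, so later use of the genotype is possible.

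Section 4.5.8 also refers sampling procedures to the laboratory manual, which is not among the documents. A pre-transplant limit may be there, but the protocol sentence as it stands says otherwise.

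A reader might go further than the documents allow in four ways:

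- **That every post-transplant sample gives the wrong genotype.** On the assumptions above most pairs agree, except for an unrelated donor at the higher allele frequency, where it is about even. Mixed chimerism may also give an ambiguous call rather than a wrong one.
- **That the error could not be detected.** Comparing the collection date with the transplant date identifies each case. The plan simply contains no such check.
- **That the planned PK or interaction analysis will contain a misclassified covariate.** No section commits to using genotype as a covariate.
- **That the schedule itself calls for genotyping after transplant.** Appendix 1, Table 3 does list "Whole blood sampling for EDTA and clinical" on Day 1 of maintenance, and a similar row appears in the post-treatment table. The label clinical is not defined there, however, and monthly draws for up to 2 years fit poorly with a one-off genotype. The point rests on Section 4.5.8.4 and does not need this reading.

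**Conclusion.** The point holds in a limited form. Section 4.5.8.4 permits a post-transplant blood sample to be recorded as the patient's CYP genotype, and no section of the protocol prevents it. The size is small: about 0.05–1.2 of 20 high-risk patients even with no catch-up sampling, and less with it, plus any in the favorable/intermediate-risk and dose-escalation groups. The missed-sample rate, transplant rate, allele frequency and donor type behind that range are all assumptions. No primary or secondary efficacy endpoint is touched. The change is still worth making, because the rule can produce a wrong value where a missing one would be preferable.

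**What to change.** In Section 4.5.8.4, keep "If the sample is missed on Day 1, it can be collected at any other scheduled visit" and continue the sentence with: *before allo-HSCT conditioning; blood collected after allo-HSCT must not be used for clinical genotyping*. Put the same limit in the laboratory manual if it is not already there.

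In any analysis that uses genotype, set to missing every result whose collection date falls after the transplant date.

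DNA from a stored pre-transplant sample could replace a missing genotype, but only where consent permits. Section 4.5.8.3 says that the biomarker research is not aimed at separating germline from somatic mutations, and storage in the biosample repository needs its own optional signature (Section 4.5.11.5).

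The cost is one sentence and one date check. The downside is that a few patients may have a missing genotype. Treatment and visits do not change.
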